2.0 OBJECTIVES AND SCIENTIFIC AIMS

The primary goal of the proposed study is to directly compare PET/CT with MRI perfusion in distinguishing between radiation injury and tumor progression. These are the two most commonly performed tests for possible radiation injury cases (MRI spectroscopy, diffusion imaging, and experimental PET/CT tracers trail far behind). There has been very little

comparative effectiveness research to determine an optimal imaging strategy, whether both are complementary and necessary, or whether one outperforms the other. This protocol will help us answer those questions, and may lead to dramatic changes in the way we and other institutions manage these diagnostic dilemmas. After the completion of radiation therapy and a follow-up MRI exam demonstrating a worsening enhancing brain lesion, patients will undergo both MRI perfusion and PET/CT exams. If the follow up MRI is a brain MRI perfusion, it will serve as both the screening scan and protocol intervention. In this case, patients will undergo only a PET/CT exam. The findings from each of these imaging studies will be used to predict whether the lesion represents tumor progression or radiation necrosis based on clinical follow-up and/or pathologic tissue sampling.

Primary Endpoint:

1. To assess the utility of PET/CT and MRI perfusion studies in predicting whether worsening enhancing brain lesions seen after radiation therapy represent radiation injury or tumor progression. This study will examine the role of these two imaging techniques in predicting diagnosis and treatment planning.

Exploratory Endpoint:

- 1. To assess the utility of PET and MRI perfusion studies in predicting tumor progression in patients with tumors with a history of brain radiation therapy receiving anti-angiogenic therapy (such as bevacizumab). Due to direct drug effects upon the vasculature, these tumors often show little or no enhancement despite clinical worsening and increasing non-enhancing abnormalities. The role of advanced imaging in determining progression in lesions that do not show increased enhancement has not been defined. In an exploratory fashion, we will enroll patients with tumors with a history of brain radiation therapy receiving anti-angiogenic therapy with suspected progression and increased nonenhancing lesions.

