3.3 Exploratory use in patients treated with anti-angiogenic therapy

Bevacizumab is an anti-angiogenic therapy that is commonly used to treat patients with malignant gliomas (usually recurrent) as well as some systemic tumors (e.g., breast). In these cases, the use of contrast enhancement to determine response as performed in daily clinical practice and as defined by many clinical protocols, is less reliable.³² This is because bevacizumab may induce rapid decreases in contrast enhancement at imaging not accompanied by actual reductions in tumor. An alternative imaging marker to determine tumor progression in these patients is necessary.

Several studies have described decreased perfusion and decreased enhancement after anti-angiogenic therapy.³³⁻³⁵ This has been postulated to be due to normalization of the blood-brain barrier rather than decreased tumor burden. The exploratory endpoint concerns the growing use of anti-angiogenesis therapy (such as bevacizumab) in brain

tumor patients. Although direct effects on the vasculature may also affect perfusion, the precise effects involved remain poorly understood. The effects upon FDG uptake are similarly poorly understood, although the effects on glucose metabolism may be less dramatic than the effects on the vasculature. We believe that adding these patients to an exploratory endpoint will help us improve our understanding of the imaging effects of antiangiogenic therapy and develop better imaging tools to determine tumor progression.

Exploratory Endpoint:

1. To assess the utility of PET and MRI perfusion studies in predicting tumor progression in patients with malignant gliomas receiving anti-angiogenic therapy (such as bevacizumab). Due to direct drug effects upon the vasculature, these tumors often show little or no enhancement despite clinical worsening and increasing non-enhancing abnormalities. Therefore, we often cannot rely on changes in size of the contrast enhancing mass lesion as usual. The role of advanced imaging in determining progression in lesions that do not show increased enhancement has not been defined. In an exploratory fashion, we will enroll patients with malignant gliomas receiving anti-angiogenic therapy with suspected progression and increased nonenhancing lesions. Analysis will be similar to that for patients under the Primary Endpoint.

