Specifically, to be classified as radiation injury, the lesion must spontaneously stabilize (stable disease) or decrease (partial response or complete response) on subsequent scans over a minimum of 6 months without new chemotherapy. Lesions that continue to increase (fulfilling criteria for progressive disease) will be considered tumor. If the lesion is stable for <6 months and therefore does not meet above criteria for radiation injury, it will be placed in a third category of uncertain and may be excluded from statistical analysis, unless additional follow up beyond the 6 months shows stability (radiation injury) or enlargement (worsening tumor). Therefore, the designation of uncertain may be only temporary, as we will continue to follow the lesion and the patient whenever possible. If a lesion has an uncertain diagnosis despite continued follow up at the end of the study, it will also be placed in the uncertain category and may be excluded from statistical analysis.

Patients with metastatic disease who have enhancing lesions and receive chemotherapy for systemic disease may be determined to have radiation necrosis if: 1) the systemic chemotherapy does not change during the 6 month follow up period to establish radiation necrosis; and 2) the systemic chemotherapy has no known efficacy for CNS disease. If the lesion diagnosis is uncertain after follow up for reason, including interval changes in systemic chemotherapy or additional radiation therapy for new lesions (unrelated to the initially treated lesion that is being followed) as per their treating physician and the

^{*}Progression occurs when this criterion is present.

florease in corticosteroids alone will not be taken into account in determining progression in the absence of persistent clinical deterioration.

standard of care, then the treated lesion will be placed in the third category of uncertain and excluded from statistical analysis.

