11.2 Subcohort analyses

The patients will also be grouped according to the following clinical scenarios:

- 1) Gliomas after radiation therapy with increased or new enhancing lesions
- 2) Gliomas after radiation therapy in patients receiving bevacizumab or other antiangiogenic chemotherapy with increased or new enhancing and/or non-enhancing lesions
- 3) Metastases after radiation therapy with increased or new enhancing lesions
- 4) Metastases after radiation therapy who may be receiving bevacizumab or other antiangiogenic chemotherapy for systemic or brain disease

Although we anticipate similar changes in MRI perfusion and PET/CT for radiation injury (smaller values) vs. tumor (larger values) regardless of the clinical scenario, it is possible for different results to occur in gliomas vs. metastases, or initially treated vs. recurrent disease. Each scenario encompasses similar tumor types that are expected to receive similar standardized radiation therapy plans (in terms of dose, fractionation and schedule). For each subcohort of patients, we will determine the efficacy of MRI perfusion and PET/CT in predicting radiation injury vs. tumor progression in an exploratory fashion.

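### For lesions followed on anti-angiogenic therapy, the follow-up rule leaves the radiation-injury label ambiguous, unavailable or unaddressed, so the planned injury-versus-tumor analyses of this subset lack a dependable injury class outside histology

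*Combined protocol and SAP*

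**What the plan says.** Section 7.3 sets the reference standard when there is no histology. For an injury label, "the lesion must spontaneously stabilize (stable disease) or decrease (partial response or complete response"), and this must hold "on subsequent scans over a minimum of 6 months without new chemotherapy". For the other class, "Lesions that continue to increase (fulfilling criteria for progressive disease) will be considered tumor". Lesions that fit neither are uncertain and may be excluded.

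A second paragraph of Section 7.3 covers metastases in patients on chemotherapy for systemic disease. Injury may be assigned if "the systemic chemotherapy does not change during the 6 month follow up period to establish radiation necrosis" and if "the systemic chemotherapy has no known efficacy for CNS disease". Gliomas have no corresponding paragraph.

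Section 3.3 explains why anti-angiogenic therapy is a special case: "bevacizumab may induce rapid decreases in contrast enhancement at imaging not accompanied by actual reductions in tumor". It then says that the analysis of these patients will resemble that of the primary endpoint.

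Exploratory endpoint 1 in Section 2.0 concerns "predicting tumor progression in patients with tumors with a history of brain radiation therapy receiving anti-angiogenic therapy". Section 11.2 plans an exploratory injury-versus-progression analysis in each of four scenarios. Scenario 2 is gliomas on anti-angiogenic treatment. Scenario 4 is "Metastases after radiation therapy who may be receiving bevacizumab or other antiangiogenic chemotherapy for systemic or brain disease". Section 11.1 expects 5-10 patients on such therapy. It plans sensitivity, specificity, ROC and AUC if numbers suffice and a descriptive summary if they do not.

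**The concern.** Sensitivity, specificity and AUC need two trustworthy outcome classes. In patients defined by being on a drug that alters the images, six months of stability may reflect the drug, the absence of tumor, or both. The metastasis paragraph shows that the authors recognised this kind of confounding, but the safeguard was not extended to gliomas or to drug given for brain disease.

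The possible error has a direction. Section 3.3 reports lower perfusion after anti-angiogenic therapy and suggests that the effect on glucose metabolism may be smaller, while calling both poorly understood. If so, a drug-suppressed tumor would have low perfusion and be labelled injury. MRI perfusion would be credited and PET charged with an error, in the comparison the study was set up to make. Section 4.1 also analyses all enrolled patients as one cohort, so a wrong label would not stay within the exploratory aim.

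**Working it through.** **1. What follow-up can deliver, by situation (Section 7.3)**

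| Situation | Injury label by follow-up? |
|---|---|
| Glioma, drug continued, *spontaneously* read loosely | Yes: only new chemotherapy is barred |
| Glioma, drug continued, *spontaneously* read strictly | No: stability on an active drug is not spontaneous |
| Metastasis, unchanged systemic drug, no known CNS efficacy | Yes, explicitly |
| Metastasis, systemic drug with known CNS efficacy | No: tumor or uncertain only |
| Metastasis, drug given for brain disease | Not addressed: the two conditions concern systemic disease |

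The word *spontaneously* is not defined, so two assessors could label the same glioma lesion differently. Only the third row gives a clear route to injury.

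**2. How far histology helps.** The plan states no power or precision for this subset, so there is no figure to reproduce. Inputs: n = 5-10 (Section 11.1); histology in 15-25% (Section 11.1); injury share among labelled patients 42/(90 + 42) = 31.8% (Section 11.1). The last two are cohort-wide rates, assumed to hold here.

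- Histology cases: 5 × 0.15 = 0.75 to 10 × 0.25 = 2.5.
- Histology-proven injuries: 0.75 × 0.318 = 0.24 to 2.5 × 0.318 = 0.80.
- With p = histology rate × 0.318, P(at least one proven injury) = 1 − (1 − p)^n: 22-34% for n = 5 and 39-56% for n = 10.
- An ROC curve needs at least one lesion in each class. With h = histology rate and q = h × 0.682, P(both) = 1 − (1 − p)^n − (1 − q)^n + (1 − h)^n: 8-18% for n = 5 and 24-47% for n = 10.

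**3. Possible effect on the pooled comparison.** Section 11.1 gives a type II error of about 10% at effect size 0.5 with 150 patients. A one-sided 5% t-test reproduces this if all 150 are analysed: 8.0% (75/75), 9.0% (90/60), 11.0% (100/50). With the plan's own 90/42 split it is 15.5%, that is 84.5% power, which is the baseline here.

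Let k of the 42 injury labels be tumors, on a metric where they look like tumor. The effect size becomes 0.5 × (1 − k/42).

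- At the cohort injury share, follow-up would give n × (1 − histology rate) × 0.318 = 1.2 to 2.7 injury labels in this subset. If all were wrong, 2.8-6.4% of the 42 are affected, the effect size is 0.49-0.47, and power is about 83-80%.
- Ceiling, with all 5-10 patients being tumors labelled injury: 12-24% of the 42, effect size 0.44-0.38, power about 76-65%.

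**4. Illustrative shift in the MRI-PET comparison within the subset.** AUC = Φ(d/√2), which is 0.69 at d = 0.7. Let a share f of injury labels be tumors with fully injury-like perfusion and fully tumor-like FDG. Then AUC(PET) = (1 − f) × AUC + f × 0.5, AUC(MRI) is unchanged, and the difference is f × (AUC − 0.5). That is 0.2 × 0.19 = 0.04 and 0.3 × 0.19 = 0.06. The values of f are assumptions. For scale, the Hanley-McNeil standard error of a single AUC of 0.69 with 3 injury and 7 tumor lesions is about 0.18.

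**The case against.** A reader might infer that the rule can never give a valid injury label under anti-angiogenic therapy, that scenario 4 has no injury class, and that the exploratory endpoint cannot be answered. The documents do not support any of these.

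- *Spontaneously* is ambiguous, not permissive. Read strictly, it withholds the injury label from a lesion held stable by a drug. This stands against any claim that stability on the drug simply counts as injury. It does not rescue the analysis, because the strict reading leaves gliomas on continued drug with no follow-up injury class.
- The adopted response criteria require every row for stable disease, including T2/FLAIR and clinical status. Reduced enhancement alone is therefore not enough, and non-enhancing growth can count as progression. This is real but partial protection: it catches progression, but does not show that a stable lesion was injury.
- The drug effect quoted from Section 3.3 is a rapid fall in enhancement. Patients in scenario 2 enter with a worsening lesion while already on the drug, and nothing in the documents says that later stability is the same artefact. This stands: mislabelling is possible, not demonstrated.
- Scenario 4 includes metastases on an unchanged systemic drug with no known CNS efficacy, which can be labelled injury. Drug given for brain disease is unaddressed, not barred. Both points stand.
- The analysis is exploratory, with a descriptive fallback. This stands and limits the importance, although a descriptive table also needs an outcome that means something.
- Progressed versus not progressed does not stop the drug from influencing both the scans and the outcome. This stands. The gain is that a suppressed, stable lesion is correctly called not progressed, where it might otherwise be wrongly called injury.

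**Conclusion.** The concern holds in limited form. Outside histology, the reference standard is ambiguous for gliomas on a continued anti-angiogenic drug, yields no injury label for metastases on a systemic drug with known CNS efficacy, and is silent on drug given for brain disease. The injury-versus-tumor accuracy analyses for scenario 2 and part of scenario 4 therefore lack a dependable injury class. Less than one histology-proven injury is expected.

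Progression labels remain available, so the exploratory endpoint as worded in Section 2.0 can still be addressed.

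The reach is small: 5-10 expected patients in an exploratory aim, plus a possible loss of a few percentage points of pooled power (up to about 20 at an unlikely ceiling). These sizes assume that the 5-10 figure covers scenarios 2 and 4 together, and that cohort-wide histology and injury rates apply. The documents give no subgroup rates. The AUC shifts depend on an assumed f, are well below the sampling error in so few lesions, and should be read as direction only.

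**What to change.** Reconcile Sections 3.3, 7.3, 11.1 and 11.2 before labels are assigned.

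1. For lesions followed while on anti-angiogenic therapy, make the outcome progressed versus not progressed at 6 months by the adopted response criteria. State the starting point, for example the later study scan. Run the planned accuracy analyses on that outcome, descriptively if numbers are small.
2. For lesions on a drug with known or possible CNS effect, use the radiation-injury label only when histology shows it. Metastases on an unchanged systemic drug with no known CNS efficacy can keep the existing rule.
3. In the pooled injury-versus-tumor analysis, either include the affected patients only with histology labels or report the result with and without them. Otherwise they could enter only as tumors, which is its own distortion.

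This changes outcome classification and analysis only; treatment and follow-up are untouched and no new data are needed. The cost is protocol and SAP wording, a few lesions leaving the pooled analysis, and a conclusion for this subset that concerns progression, not injury.

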1.0 PROTOCOL SUMMARY AND/OR SCHEMA

Some patients treated with brain radiation therapy for tumors located in the head may develop new or increased enhancing mass lesions. These worsening lesions may represent radiation injury/necrosis or tumor progression. This study will examine the utility of MRI perfusion and FDG PET/CT to determine if the enhancing lesions represent radiation injury or tumor progression. Both MRI perfusion and FDG PET/CT scans are part of the standard of care for patients with indeterminate lesions after treatment. The purpose of this study is to prospectively enroll these patients in order to determine if MRI perfusion or FDG PET/CT performs better in predicting if a worsening enhancing brain lesion represents radiation injury or tumor progression. In addition the entire cohort analyses, subcohort analyses will be performed for patients belong to specific clinical scenarios and compared using an interaction test.

Prior to enrolling in the study, each patient will have a CT or MRI scan that shows an increasing indeterminate mass lesion. If the screening scan is a brain MRI perfusion, it can also function as the protocol intervention.

Screening (within 12 weeks of enrollment): Neurological and/or physical examination

Intervention: Brain MRI perfusion and PET/CT performed within 12 weeks of each other. Either MRI perfusion or PET/CT may be performed first. The first of the two scans should be performed within 12 weeks after the screening scan showing an increasing indeterminate mass lesion. If the screening scan is a brain MRI perfusion, it can also function as the protocol intervention. Imaging based diagnosis of radiation injury vs. worsening tumor will be rendered by a study neuroradiologist and by a nuclear medicine radiologist and entered into a secure database.

*Note that clinical reads of the MRI perfusion and PET/CT will be rendered as per the standard of care, usually within 24-48 hours after completion of the study. These reports get dictated in Powerscribe and then become part of the patient's electronic medical record.

Off study: Patients will remain on study until the completion of either the MRI perfusion or PET/CT that are within 12 weeks of each other. After one of these scans, the patient will have no active interventions and will be off study. Patients will obtain a standard of care brain MRI scan about every 2-3 months. These MRI scans will be used to track disease progression.

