10.0 CRITERIA FOR REMOVAL FROM STUDY

- 1. Inability to undergo MRI (e.g., pacemaker, claustrophobia) or PET/CT scan
- 2. Found to be ineligible for the protocol as described in the section on Criteria for Patient/Subject Eligibility
- 3. Patient and/or guardian requests to withdraw from study for any reason
- 4. Referring physician requests to withdraw from study for any reason, including believing that it would be in the patient's best interest
- 5. Refusal of patient to continue treatment and/or observations
- 6. Loss to follow-up
- 7. Patient death, unless an autopsy is performed to render a diagnosis of the indeterminate brain lesion

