11.1 Entire cohort analyses

Despite the heterogeneity of potential tumor types, radiation injury has a common mechanism in all patients: blood brain barrier disruption, inflammation, gadolinium contrast leakage into the interstitial space, and enhancement. In most clinical scenarios, we expect lower MRI perfusion and lower FDG PET/CT measurements for radiation injury regardless of the original tumor type. When considering the target accrual of 150 patients with indeterminate lesions, we anticipate that tumor progression will occur more commonly (approximately 90 patients) than radiation injury (approximately 42 patients) or uncertain diagnoses (approximately 8 patients). We anticipate that only 20-30% (28-42 patients) will require the entire 6 month follow up period to establish their diagnosis. Some patients may require >6 months and be followed up to 1 year to establish their diagnosis. Loss to follow up or death prior to determining a definitive diagnosis is expected to be uncommon (<5 patients). Unless an autopsy is performed to render a diagnosis for the brain lesion, death will be a criterion for removal from the study as described in Section 10.

We will perform one-sided two-sample t-tests (because previous analysis showed that MRI perfusion measurements are reasonably symmetric, have a small range and are usually lower in radiation injury than in tumor progression). To approximately assess the power of the analysis, we focus on the one-sided two sample t-test with the type I error

(claiming a difference while there is not) rate of 5%. With 150 patients over 2 years and assuming the effect size is 0.5 (meaning that the difference is half of the pooled standard deviation), type II error (failure to detect a difference that actually exists) rate is about 10%. If the effect size is 0.7, the type II error rate is about 1%. Here we used generic mean/standard deviation ratios because multiple measurements will be examined.

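### Lesions with an uncertain label are dropped under inconsistent rules with no check on the effect, so each modality's accuracy may be biased; the effect on the PET-versus-MRI difference is likely small

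*Combined protocol and SAP*

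**What the plan says.** **Exclusion of uncertain lesions.** Section 7.2 excludes lesions whose pathology stays unclear. In Section 7.3, a lesion stable for less than 6 months is treated differently: "it will be placed in a third category of uncertain and may be excluded from statistical analysis". The same option applies to lesions still uncertain at the end of the study. The last paragraph of 7.3, which covers changes in systemic chemotherapy and radiation for new lesions, makes exclusion unconditional again.

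**The injury label.** By follow-up, the lesion must stabilize or shrink "on subsequent scans over a minimum of 6 months without new chemotherapy". Growth meeting the progression criteria is labelled tumor.

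**Who sees the scans.** Section 1.0 says of the clinical reads: "These reports get dictated in Powerscribe and then become part of the" patient's record. Section 7.3 accepts that the treating physician's notes may mention them. Section 4.1 leaves treatment to that physician, and Section 3.4 says that establishing progression can directly affect therapy. Section 4.2 requires both scans before any treatment change.

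**Deaths.** Section 10 item 7 lists as a removal criterion: "Patient death, unless an autopsy is performed to render a diagnosis of the indeterminate brain lesion". Section 11.1 speaks of loss or death before a definitive diagnosis (fewer than 5 patients), then repeats the removal rule without that limit.

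**Expected numbers.** Section 11.1 expects about 90 tumor progressions, about 42 radiation injuries and "uncertain diagnoses (approximately 8 patients").

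**The concern.** Consider an injury lesion with a positive scan. If the physician acts on the report and starts chemotherapy, and the lesion then stabilizes, it cannot meet the injury rule. It has not grown, so it is not tumor either. By elimination it becomes uncertain and can leave the analysis. Such lesions are false positives, and losing them makes a test look more specific than it is.

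Other losses act differently. Losing scan-positive tumors removes true positives, which lowers sensitivity. At stake are each modality's sensitivity, specificity and AUC and, if clinicians act on one modality more than the other, the comparison between them.

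Two defects of wording stand apart from any bias argument. An optional exclusion lets the analysis set be settled after scan results are known. And because follow-up runs until death (Sections 1.0 and 4.1), Section 10 item 7 read literally also removes patients who die after a label was assigned.

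**Working it through.** **1. The plan's own figure.** Section 11.1 states: "We will perform one-sided two-sample t-tests", with a type I error ("claiming a difference while there is not) rate of 5"%). It continues: "With 150 patients over 2 years and assuming the effect size is 0.5", the type II error is about 10%.

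- Formula: power ≈ Φ(d / √(1/n₁ + 1/n₂) − 1.645).
- All 150 split 42:90 gives n₁ = 150 × 42/132 = 47.7 and n₂ = 102.3. Then Φ(2.852 − 1.645) = Φ(1.207) = 0.886, a type II error of 11.4%. This reproduces the plan's figure.
- The patients expected to have a label are 42 and 90: Φ(2.676 − 1.645) = Φ(1.031) = 0.849, a type II error of 15.1%.

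At that split, the stated figure needs all 150 patients in the analysis. The expected counts sum to 90 + 42 + 8 = 140, so 10 of the 150 are not accounted for.

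**2. Share at risk.** From 8/150 = 5.3% (uncertain only) to (8 + 5)/150 = 8.7% (adding the upper limit for early loss or death).

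**3. Bounds.** These treat each patient as one lesion. Observed accuracy is an assumption.

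- Specificity observed at 34/42 = 81%, all 8 uncertain counted as injury: 34/50 = 68% if all 8 are scan-positive, (34 + 8)/50 = 84% if all are scan-negative.
- Sensitivity observed at 72/90 = 80%, all 8 counted as tumor: 72/98 = 73.5% if all are scan-negative, 80/98 = 81.6% if all are scan-positive.

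**4. Simulated AUC, extreme case.** Assumptions: one normally distributed metric per modality, tumor and injury means 1.19 SD apart (true AUC 0.80 for both), cut-off at the midpoint, 90 tumor and 50 injury lesions. Eight PET-positive injury lesions are then removed.

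| PET–MRI correlation | Implied concordance | PET AUC | MRI AUC | False difference |
|---|---|---|---|---|
| 0.3 | 67% | 0.86 | 0.82 | 0.041 |
| 0.6 | 76% | 0.86 | 0.83 | 0.027 |
| 0.8 | 83% | 0.86 | 0.84 | 0.014 |

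Section 11.1 expects concordance above 80%, so only the last row fits the plan. The standard error of the difference there is about 0.026, and 0.014/0.026 ≈ 0.5.

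**5. Less extreme cases, correlation 0.8.**

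- Eight injury lesions lost because either scan was positive: both AUCs read about 0.84, with a difference near 0.
- Four tumor and four injury lesions lost among PET-positives: the difference is 0.004 to 0.006.
- All eight lost lesions PET-positive tumors: PET AUC falls to about 0.79 and the difference is about −0.002.
- PET-positive tumor and injury lesions equally likely to be lost (90:42 mix, 5.7% to 12% excluded): AUCs stay at 0.80, but PET sensitivity falls from 0.724 to between 0.703 and 0.676, and specificity rises from 0.724 to between 0.744 and 0.768.
- Random loss: no bias.

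**The case against.** The strongest reply is that the causal chain is inferred. No section says treatment follows the scan result. The optional-exclusion sentence concerns short follow-up, and Section 7.3 adds that the uncertain label may be temporary. The treatment reasons named there are systemic chemotherapy changes and radiation for new lesions unrelated to the study lesion. A positive scan may also lead to resection, which normally gives a pathology label and keeps the lesion in. Few lesions are expected to be lost.

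Most of this stands as a limit on size and certainty, but it does not close the path:

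- Blinding the outcome assessor does not help, because the path runs through the unblinded treating physician.
- Longer follow-up can resolve a short observation period, but it cannot undo new chemotherapy.
- Raising accrual, the response offered in Section 11.1, restores numbers but not the lost lesions.
- The pathology-versus-follow-up comparison contains only labelled lesions.

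Three stronger readings are tempting and not supported. A reader might infer that the exclusions always inflate accuracy; the direction depends on which lesions are lost. A reader might infer a material false advantage for one modality; that needs one-sided, near-complete selection and concordance below what the plan expects. A reader might infer that labelled patients who later die will be deleted; Section 11.1 twice refers to death before diagnosis, so this is mainly a wording conflict.

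**Conclusion.** The concern holds in limited form. The exclusion rule is inconsistent and partly discretionary, and nothing planned shows its effect. Each modality's own accuracy is the main exposure: specificity could lie between 68% and 84% against an observed 81%, and an AUC of 0.80 could read about 0.86 in the extreme case. The false difference between modalities is about 0.014 in that case at the plan's expected concordance, and near 0 if either scan drives the loss.

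These sizes rest on the plan's 42 and 8 patients and its concordance figure. The assumed observed accuracy, true AUC, normal metrics and selection patterns are illustrations, not document figures. That treatment depends on the scans is plausible from Sections 1.0, 3.4, 4.1 and 7.3 taken together, but it is not stated.

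**What to change.** - **Sections 7.2, 7.3 and 11.1:** replace the optional wording with one fixed rule. The primary analysis uses all lesions with a reference label. Every uncertain lesion and every pre-diagnosis death with both scans is tabulated by PET result, MRI result and reason for having no label.
- **Section 11.1:** prespecify a sensitivity analysis of each modality's sensitivity, specificity and AUC, and of the AUC difference, first with all uncertain lesions counted as tumor and then with all counted as injury. Multiple imputation of the label is optional.
- **Section 10 item 7:** add *before a reference label has been assigned*, to agree with Section 11.1.

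The cost is some protocol wording and a few analyses on data already collected; patient care is unchanged. The downside is that the reported accuracy ranges may look less favourable.
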